Appendix A. Email Instructions for use of the Interactive Anesthesia Education Program

To the Parent/Guardian of _____:

Thank you for your participation in this study. Please refer to the below instructions for using the PIRA program.

Access to the education program is by a computer or tablet device through the hyperlink included below on the Google Chrome browser ONLY. Please note, a mobile device and other internet browsers will not work with this online tool.

Along with the hyperlink, we have also provided you with a unique username and password. Once you click on the hyperlink, you will be prompted to enter this information to access the program.

Link:

Username:

Password:

When you are ready to review the education materials, click, “start at the beginning” You or your child will be required to periodically answer questions or respond by clicking the mouse to move it forward. Either you or your child can click, but please make sure that both you and your child are able to see and hear the teaching the entire time.

If you need to stop for a prolonged period of time for whatever reason, you can start at the beginning again to ensure no content is missed. Refreshing the page will reset the program. It will not save where you left off.

You will receive one email reminder a few days prior to your child’s surgical date reminding you to complete the PIRA at least once with your child. If you have any problems accessing the education program, or any issues during its use, please contact the study PI, [name], at [contact] or [contact].

Thank you,

[name]

Appendix B. Parental PIRA Survey

Please complete the survey, below. Your responses to the following questions will better help us to understand how to improve our preoperative education and communication for parents and their children. As a study participant, you were randomly assigned to either receive an online interactive tool focused on educating children, named PIRA, or you received our standard preoperative information. If any of the below questions make you uncomfortable, please leave them blank.

Demographics:

Q1. Your current age (in years):

Q2. Gender:

Q3. Ethnicity:

Q4. Highest level of education achieved:

Pre-Operative Education Experience:

Q1. What of the following statements describes your experience with the anesthesia education agent, Ira? (Select all that apply)

- I did not receive the link to Ira
- I received the link to Ira, but did not watch it
- I received the link to Ira, but a different care provider or family member watched Ira.
- I watched Ira WITHOUT my child
- I watched Ira WITH my child
- I had a hard time using Ira
- My child liked using or watching Ira
- My child seemed LESS stressed about surgery or anesthesia because they watched Ira
- My child seemed MORE stressed about surgery or anesthesia because they watched Ira
- I understood anesthesia better after watching Ira
- Ira helped me talk to my child about anesthesia and surgery
- Ira helped answer questions about anesthesia
- I felt less stressed about surgery or anesthesia because I watched Ira
- Ira made my surgery experience BETTER
- Ira made my surgery experience WORSE

- Ira was difficult to use or understand

Q2. In total, about how long did you spend with the interactive education agent, Ira?

- Less than 5 minutes
- 5-30 minutes
- 30-60 minutes
- More than 60 minutes
- I did not view the agent

Q3. How likely are you to recommend the interactive education agent, Ira, to future families? (Skip if you did not receive or view Ira)

This is a sliding scale

0 = Not at all Likely to Recommend-----100 = Extremely likely to recommend

Q4. Write any topics that were missing, unclear, or absent from the interactive education agent, Ira. (Skip if you did not receive or view Ira)

**Free Text Response_____

Q5. Write any suggestions for future improvements to the interactive education agent, Ira. This may include any difficulties in accessing or using it. (Skip if you did not receive Ira)

**Free Text Response_____

Q6. Self-evaluation questionnaire. Rate the following statements how they apply to you from 1 = Not at all to 4 = Very Much So

	1 = Not at all	2 = So me wh at	3 = Mo der y at	4 = Ver atel ch so
I feel calm				
I feel secure				
I am tense				
I feel strained				

I feel at
ease

I feel
upset

I am
presently
worrying
over
possible
misfortu
nes

I feel
satisfied

I feel
frightene
d

I feel
comforta
ble

I feel
self-
confiden
t

I feel
nervous

I am
jittery

I feel
indecisiv
e

I am
relaxed

I feel
content

I am
worried

I feel
confused

I feel steady	
I feel pleasant	

Figure 1. Modified Yale Preoperative Anxiety Scale (mYPAS) for Child Anxiety

Domain: Activity

1. Looking around, curious, playing with toys, reading (or other age-appropriate behavior); moves around holding area/treatment room to get toys or go to parent; may move toward OR equipment
2. Not exploring or playing, may look down, may fidget with hands or suck thumb (blanket); may sit close to parent while waiting, or play has a definite manic quality
3. Moving from toy to parent in unfocused manner, non-activity-derived movements, frenetic/frenzied movement or play; squirming, moving on table, may push mask away
4. Actively trying to get away, pushes with feet and arms, may move whole body; in waiting room, running around unfocused, not looking at toys or will not separate from parent

Domain: Vocalizations

1. Reading (nonvocalizing appropriate to activity), asking questions, making comments, babbling, laughing, readily answers questions but may be generally quiet; child too young to talk in social situations or too engrossed in play to respond
2. Responding to adults but whispers, "baby talk," only head nodding
3. Quiet, no sounds or responses to adults
4. Whimpering, moaning, groaning, silently crying
5. Crying or may be screaming "no"
6. Crying, screaming loudly, sustained (audible through mask)

Domain: Emotional Expressivity

1. Manifestly happy, smiling, or concentrating on play
2. Neutral, no visible expression on face
3. Worried (sad) to frightened, sad, worried, or tearful eyes
4. Distressed, crying, extremely upset, may have wide eyes

Domain: State of Apparent Arousal

1. Alert, looks around occasionally, notices/watches anesthesiologist (could be relaxed)
2. Withdrawn child sitting still and quiet, may be sucking on thumb or face turned in to adult
3. Vigilant looking quickly all around, may startle to sounds, eyes wide, body tense
4. Panicked whimpering, may be crying or pushing others away, turns away

Figure 2. Parental State-Trait Anxiety Inventory (STAI) for Parental Anxiety

Self-evaluation questionnaire	STAI Form Y-1			
	1	2	3	4
1. I feel calm				
2. I feel secure				
3. I am tense				
4. I feel strained				
5. I feel at ease				
6. I feel upset				
7. I am presently worrying over possible misfortunes				
8. I feel satisfied				
9. I feel frightened				
10. I feel comfortable				
11. I feel self-confident				
12. I feel nervous				
13. I am jittery				
14. I feel indecisive				
15. I am relaxed				
16. I feel content				
17. I am worried				
18. I feel confused				
19. I feel steady				
20. I feel pleasant				

1: Not at all, 2: Somewhat, 3: Moderately so, 4: Very much so

Figure 3. PACU Pediatric Anesthesia Emergence Delirium (PAED) for Anesthesia**Emergence Delirium**

Behavior	Not at all	Just a little	Quite a bit	Very much	Extremely
The child makes eye contact with the caregiver	4	3	2	1	0
The child's actions are purposeful	4	3	2	1	0
The child is aware of his/her surroundings	4	3	2	1	0
The child is restless	0	1	2	3	4
The child is inconsolable	0	1	2	3	4

K. References

- Akdağ, M. (2014). A multi-centric prospective study: Anxiety and associated factors among parents of children undergoing mild surgery in ENT. *Journal of Clinical and Experimental Investigations*, 5(2), 206–210.
- Aytekin, A., Doru, Ö., & Kucukoglu, S. (2016). The effects of distraction on preoperative anxiety level in children. *Journal of Perianesthesia Nursing: Official Journal of the American Society of Peranesthesia Nurses / American Society of Peranesthesia Nurses*, 31(1), 56–62.
- Bartik, K., & Toruner, E.K. (2017). Effectiveness of a preoperative preparation program on children's emotional states and parental anxiety. *Journal of Perianesthesia Nursing: Official Journal of the American Society of PeriAnesthesia Nurses / American Society of PeriAnesthesia Nurses*. <https://doi.org/10.1016/j.jopan.2017.09.008>
- Beringer, R. M., Greenwood, R., & Kilpatrick, N. (2013). Development and validation of the Pediatric anesthesia behavior score - an objective measure of behavior during induction of anesthesia. *Pediatric Anesthesia*, 24(2), 196–200.

- Buckley, A., & Savage, E. (2010). Preoperative information needs of children undergoing tonsillectomy. *Journal of Clinical Nursing*, 19(19-20), 2879–2887.

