Anecdotally, parents frequently report a lack of understanding or a plan for how to address the idea of surgery and anesthesia to their child. This has been especially problematic in school-age children, who may lack the ability to anticipate and comprehend the necessary issues, solutions, and consequences. Evidence supports the benefits of enhanced preoperative education for pediatric patients and families. This, coupled with the lack of developed interactive agents preparing the pediatric patient and family for the perioperative anesthesia experience, demonstrated a need for the creation of such tools. This PIRA was developed by perioperative clinical experts, including perioperative Registered Nurses (RNs), Certified Registered Nurse Anesthetists (CRNAs), Physician Anesthesiologists, and Child Life Specialists (CLS) all with greater than two years' clinical experience, in addition to nonmedical parents. Piloting this intervention in a randomized controlled trial (RCT) to determine its impact on pediatric and parental anxiety, satisfaction, likelihood to recommend to others, and emergence from anesthesia, is critical for successful implementation and potential future iterations.

Given the large anesthetic volume at Boston Children's Hospital (BCH), this PIRA intervention has the ability to positively impact tens of thousands of patients and families to adjunct the preoperative process to reduce anxiety, provide knowledge in regards to the perioperative anesthesia experience (preoperative, intraoperative and postoperative), enhance communication between the child and parent (encourage questions, explanations as it relates to the perioperative experience), prevent post-operative maladaptive behavior (POMB), and increase parental satisfaction with the perioperative experience. Testing these potential benefits while adjusting the PIRA based on user feedback is essential for maximizing the impact and

dissemination of the tool. Moving forward, expanding the PIRA to include additional languages, a wider developmental age range, different anesthetic options other than general anesthesia, and including anesthetic locations outside of the operating room—such as radiology, procedural rooms, wound care, gastroenterology, or the emergency department—will further enhance these benefits and include more families.

C. Preliminary Studies

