If there were problems surrounding the accessibility, content, language, or any other system issues, this will affect utilization and the PIRAs future potential impact.

Regardless of the medium, materials, or content provided, no preoperative educational program can be successful and sustainable unless readily adopted and utilized by parents and children. As such, a primary outcome will evaluate whether families actually viewed the materials, with whom, and how much time they spent with the PIRA.

Parental Perceived Impact and Impressions:

- *Did parents find the tool subjectively helpful?*
- *What improvements or changes in content or language would they consider?*
- *Would parents recommend the PIRA to future families?*

Identifying parental perceived benefits or drawbacks to the PIRA may elucidate the familial interactions and how they feel about their educational experience in a different way than anxiety or other objective data. Similarly, given the novel nature of the PIRA, it is important to identify any educational gaps and potential for future topics and educational needs. If parents believe the PIRA improved their preoperative experience, it could be useful for future families.

Secondary Outcomes

Child Anxiety in Preoperative Waiting:

As discussed, more than 60% of pediatric patients have been found to suffer from anxiety in the preoperative period. The effects of anxiety may have behavioral sequelae, or Postoperative Maladaptive Behaviors (POMB), which can last up to a year or longer. Therefore, reducing anxiety levels should be a priority of any educational tool for pediatrics. Numerous randomized control trials have demonstrated decreased child anxiety in preoperative waiting for those patients who participated in preoperative educational programs including videos, tours, apps, games, and books. *Is there a similar difference in the control and intervention groups' preoperative anxiety with this PIRA intervention?*

Parental Anxiety in Preoperative Waiting:

In several cited studies, parental anxiety directly correlates with the pediatric patient's anxiety. Thus limiting or reducing parental anxiety is an important part of a preoperative education intervention. *Does improved communication and education decrease parental anxiety?* An intervention which serves to improve communication between the parent/child as well as the parent/anesthesia provider AND reduce parental anxiety would perhaps provide significant benefits.

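### Appendix B Q1 asks about the child's stress in both directions but about the parent's own stress only as a reduction, so a parent-perceived increase attributed to PIRA cannot be counted

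*Combined protocol and SAP*

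**What the plan says.** Section D(4) lists Parental Perceived Impact and Impressions under the primary outcomes and explains its purpose: "Identifying parental perceived benefits or drawbacks to the PIRA may elucidate the familial interactions". It adds that the outcome should show "how they feel about their educational experience in a different way than anxiety or other objective data". Section D(5) says that this outcome is assessed with the Appendix B survey.

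Q1 of that survey is a list of statements with the instruction to select all that apply. On stress attributed to the tool it contains:

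- for the child, a statement of less stress and its opposite, "My child seemed MORE stressed about surgery or anesthesia because they watched Ira";
- for the parent, only "I felt less stressed about surgery or anesthesia because I watched Ira".

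The surgery experience as a whole also appears in both directions: "Ira made my surgery experience BETTER" and "Ira made my surgery experience WORSE".

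The other survey questions cover time spent (Q2), likelihood to recommend (Q3), missing or unclear topics (Q4), suggestions for improvement (Q5, with the prompt "This may include any difficulties in accessing or using it") and the state-anxiety items (Q6). Section B says that "adjusting the PIRA based on user feedback is essential for maximizing the impact".

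**The concern.** The same construct, stress attributed to the tool, is measured two-sidedly for the child and one-sidedly for the parent. An educational tool about anesthesia could plausibly reassure some parents and worry others. As the form stands, the first group has a box and the second does not.

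At stake is the usefulness of the feedback rather than any hypothesis test. If some parents were made more anxious by the content, the developers would want to know how many, because the protocol intends to revise the tool from user feedback. A report giving only the share who felt less stressed would leave the reader unable to say anything about the remainder.

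**Working it through.** The check is mainly a reading of the form. Only two small calculations apply, and the plan states no figure on this point to reproduce.

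**Step 1. Classify the Q1 options by subject and direction.**

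| Subject | Favourable | Unfavourable |
|---|---|---|
| Child's stress because of the tool | 1 | 1 |
| Surgery experience overall | 1 | 1 |
| Parent's own stress because of the tool | 1 | 0 |
| Child liked it; parent understood anesthesia better; helped parent talk to child; helped answer questions | 4 | 0 |
| Hard time using it; difficult to use or understand | 0 | 2 |

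Five further options record receipt and viewing. Total: 2 + 2 + 1 + 4 + 2 + 5 = 16, which is the full list. The list therefore mixes paired and unpaired items. The relevant comparison is between the first and third rows: same construct, different person, different treatment.

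**Step 2. Look for the missing direction elsewhere in the survey.**

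- The general worse-experience option does not name stress.
- A low recommendation score (Q3) gives no reason.
- Q4 and Q5 are free text about topics, improvements and difficulties of access or use. A parent may volunteer stress there, but nobody is asked, so the answers give no usable count.
- The Q6 state-anxiety items do not mention the tool. They give a level that can be compared between arms, not the parent's own attribution.

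**Step 3. What the existing box can tell the reader.** Let n be the number of parents who watched the tool and k the number who tick the less-stressed box. If nobody who ticks it also felt more stressed, Q1's parental-stress item allows the number who felt more stressed to be anything from 0 to n − k. Take n = 30, the evaluable number per group in section I, as an illustration with one parent per family. The range is then 0 to 30 − k, and nothing in that item narrows it.

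**Step 4. What an added box would give.** The number ticking it is observed directly. If none of n parents ticks it, the one-sided exact 95% upper limit for the proportion is 1 − 0.05^(1/n):

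- n = 30: 1 − 0.05^(1/30) = 9.5%
- n = 38 (recruited per group, section I): 1 − 0.05^(1/38) = 7.6%

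These limits assume one independent respondent per family and that every affected parent ticks the box. Section D(3) gives surveys to both parents when both have consented and are present, so the independence assumption may fail. Under-ticking would make the limits too low.

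**The case against.** The strongest reply is that the gap is marginal. Section D(4) puts three questions under perceived impact: whether parents found the tool helpful, what they would change, and whether they would recommend it. Parental stress is not among them. Table 1 lists utilization, recommendation and gaps as primary, and places parental anxiety under secondary, measured by the STAI in both arms. Other routes exist too: the worse-experience box, separate boxes for usability and child stress that help interpret it, free text, the invitation in Appendix A to contact the investigator about problems, and the adverse-event provision in section E. All of this is correct and limits the size of the point. It does not supply the missing count.

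Three stronger readings are tempting, and the documents do not support them.

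- A reader might infer that the survey's result on parental stress can only favour PIRA. It cannot be put that way: few ticks of the less-stressed box would not favour the tool, and the randomized STAI comparison can go in either direction.
- A reader might infer that Q1 is a set of matched pairs with a single partner missing. It is not. The statement about understanding anesthesia better is also directional and unpaired, and the two usability items are unfavourable only.
- A reader might infer that a primary outcome is compromised. Perceived impact is headed as primary in D(4), but parental stress is one unlisted component of the survey and has no primary row in Table 1.

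**Conclusion.** The point holds in a narrow form. Q1 can count parents who perceived a reduction in their own stress because of PIRA. It cannot count parents who perceived an increase, although the stated purpose covers drawbacks and the form asks the same question of the child in both directions. No other item counts such parents.

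The size is small: one absent option in a descriptive list. It leaves the mYPAS comparison, the sample size and the Table 1 primary measures unaffected. The conclusion rests on the wording of the form alone and needs no assumption about how many parents are affected, which the documents do not tell us. It is a cheap improvement worth making, not a flaw that threatens the trial.

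**What to change.** Add to Q1, directly after the parent's less-stressed statement, the same statement with MORE in place of less. Report the number and percentage ticking each direction, using as denominator the parents who ticked that they watched Ira, with or without the child. Where both parents of a child respond, report one parent per family by a rule fixed in advance, or allow for the pairing in any confidence interval. This requires a non-identifying family code on each response, if there is not one already.

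If surveying has begun, record the form version and report the new item only for parents who saw it. If surveying is complete, state in the report that parental stress was asked in one direction only and that an unticked box does not mean no change.

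Cost: one extra tick-box in REDCap, one reporting line and, if the item is added mid-study, a version field and data from later parents only. One limit remains. A parent who ticks neither box may have felt no change or may have skipped the item, since the form invites parents to leave questions blank. Perceived increases would, however, become countable.

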additional preoperative educational materials or resources other than what is currently provided by their care team. This usually includes a routine phone call, text, or email from a pre-operative staff member within a few days of the child's scheduled procedure to provide basic information about fasting, when to arrive at the hospital, and anything additional that needs to be done prior to the procedure (e.g. COVID-19 testing), when applicable. Any specific information about the anesthetic will be deferred to the anesthesia team for the surgical day, per usual.

In both the intervention and control groups, if parents specifically request additional information to prepare for surgery, pre-op staff may send them the "Social Story" developed by the Autism Spectrum Center, Child Life Services, and Waltham Surgical Services. This document provides an age-appropriate step-by-step guide as to what to do and what to expect on the day of surgery.

On the day of surgery, all parents participating in the study, regardless of group assignment, will receive surveys to complete in the pre-operative holding area via REDCap®. The surveys will be given to the parent who consented to the study. If both parents are present, and both consented to the study, they will both receive surveys to complete. A research staff member trained for reliability and blinded to the study arm will assess the child for signs of anxiety in the pre-op holding area.

For both groups, once the surgical procedure is complete, and the child has gone to the PACU, Emergence Agitation/Delirium will be assessed per standard of care at Waltham by the bedside PACU nurse using the Pediatric Agitation Emergence Delirium Scale (PAED). The

research team will collect this PAED information retrospectively from the child's electronic medical record.

(4) Definition of Primary and Secondary Outcomes/Endpoints:

See Table 1 for Summary of Outcomes/Measures

Patient Demographics

Parental age, gender, ethnicity, and highest education level achieved will be collected as part of the REDCap® preoperative survey to better understand the pilot group and educational needs (Appendix B).

Primary Outcomes

Parental Utilization:

- *When provided with the opportunity to obtain more information as it relates to the perioperative experience, do parents and their children use the tool?*
- *How many times did they access the tool and for how long?*
- *Were there any barriers to accessing the PIRA tool?*

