Emergence from Anesthesia: Presence or absence of emergence agitation/delirium (ED):

Depending on the study, ED has an incidence between 10-80%, with most studies showing 30-50% of children having ED after a general anesthetic (Przybylo et al., 2003; Ringblom et al., 2018). ED can be extremely distressing for parents, delay discharge from post-anesthesia care unit (PACU), can result in injury to the patient or staff (due to uncontrolled flailing, kicking, punching), and can also potentially result in the unintentional dislodgement of intravenous catheters or other tubes (e.g. nasogastric, gastrostomy, chest, endotracheal tubes). Data have shown a reduction in ED incidence with the use of preoperative education programs (Kain et al., 2004). *Is there any effect on the incidence of ED for children who have more interactive preoperative education, such as PIRA, compared to standard information?*

(5) Data Collection Methods, Assessments, Interventions and Schedule

On the day of the surgical procedure, participating parents in both the PIRA and the control groups will receive the same in-person surveys in the preoperative holding area. Surveys will be administered via REDCap® and completed on iPads which have been given to the

parents by a member of the research team (Appendix B). In both groups, the parent(s) who consented to the study and there on the day of surgery will be given the surveys.

The surveys will have no identifying questions and will be automatically uploaded to REDCap®. They will be accessible only to members of the research team. Children will not be asked to complete any surveys but will be observed in the pre-op holding area by a member of the research team and in the PACU by a PACU nurse, as per standard of care at BCH Waltham. Both will have been trained for reliability in conducting the study-specific assessment tools.

Pediatric Anesthesia Emergence Delirium (PAED) scores will be collected retrospectively from the child's electronic medical record. All data collected will be de-identified and presented or published in aggregate. The research team will provide a finished copy of the manuscript upon request.

Primary Outcomes Data

Parental Utilization:

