The amount of time spent using the PIRA and the number of times the PIRA was accessed will be able to be collected via the program itself, stored on a secure Northeastern University Server, and will be accessible only to the study team. Each click of the mouse a user makes in the system will be timestamped and saved on the database. This information will be de-identified. Additionally, the parental survey administered by the research team member in the preoperative holding area will obtain self-reported data on PIRA access and time spent using the tool (Appendix B).

Parental perceived impact and impressions:

This outcome will be assessed in the same survey (Appendix B) as Parental Utilization. The survey will have no identifying questions and will be automatically uploaded to REDCap®, accessible only to members of the research team. Any data will be de-identified and presented in aggregate.

Secondary Outcomes Data

Child Anxiety in Preoperative Waiting:

Child anxiety will be assessed using the modified Yale Preoperative Anxiety Scale (mYPAS), an observational state anxiety measure for children containing 27 items in five categories (activity, emotional expressivity, state of arousal, vocalization, and use of parents). See Figure 1. The mYPAS has been validated for measuring childrens' anxiety (Kain et al., 1995; Kain et al., 1997). Members of the research team who will administer the mYPAS for this study will be trained for reliability. mYPAS scores range from 22.5 to 100, with higher scores indicating more anxiety.

Parental Anxiety in Preoperative Waiting:

Parental anxiety will be assessed using the State-Trait Anxiety Inventory (STAI). See Figure 2. This self-report anxiety instrument contains two separate 20-item subscales that measure trait (baseline) and state (situational) anxiety (Spielberger, 1973; Spielberger, 1983; Spielberger, 1989) This survey will take place in the preoperative holding area and will be administered in conjunction with the previous utilization/recommendation survey (Appendix B). The STAI is scored from 20-80, with higher scores indicating more anxiety.

Emergence from Anesthesia: Presence or absence of emergence agitation/delirium

(ED):

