Potential Gaps or Recommendations for Future Iterations (Primary)	Parental Survey, free text entry	See Appendix B Summarized for themes	Preoperative Waiting, self-reported.
Parental Anxiety (Secondary)	STAI	See Appendix B and Figure 2. Range 20-80, higher = greater anxiety	Preoperative Waiting, self-reported
Child Anxiety (Secondary)	mYPAS (Observational)	See Figure 1. Range 22.5-100	Preoperative Waiting, observed by a Research Assistant (RA)
Emergence from Anesthesia (ED) (Secondary)	PAED Scale (Observational)	See Figure 3. Range 0-20; Threshold for ED ≥ 12	PACU, observed by a Registered Nurse (RN) as per BCH standard of care.

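### Two survey items feeding the primary perceived-impact outcome ask about the surgery experience before the surgery has taken place

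*Combined protocol and SAP*

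**What the plan says.** **Timing.** Section D(3) states that all participating parents "will receive surveys to complete in the pre-operative holding area via REDCap" on the day of surgery. Section D(5) repeats this for both arms: they "will receive the same in-person surveys in the preoperative holding area". Table 1 gives preoperative waiting as the time for utilization, recommendation and content gaps, all three labelled primary. No later parent survey or contact is described. The only outcome measured after surgery is the PAED, a secondary outcome scored by the PACU nurse and taken from the chart.

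**Instrument.** Section D(4) lists perceived impact and impressions among the primary outcomes. On how it is measured, D(5) says: "This outcome will be assessed in the same survey (Appendix B) as Parental Utilization".

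**Items.** Appendix B, Q1 of the education-experience part, is a select-all list of 16 statements. Two of them concern the surgery experience: a BETTER statement and its counterpart, "Ira made my surgery experience WORSE". Q3 is a sliding-scale recommendation. Q4 and Q5 are free text on missing or unclear topics and on improvements.

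**Construct.** D(4) describes the benefit parents may perceive as an improvement in their preoperative experience. The Background (section B) is broader: among the things the tool could do, it lists to "provide knowledge in regards to the perioperative anesthesia experience (preoperative, intraoperative and postoperative").

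**The concern.** Both statements are in the past tense and name an event that has not occurred when the parent reads them. Parents must decide for themselves what is meant. Some may answer on how they expect the day to go, some on the wait so far, and some may leave both boxes empty because they cannot yet say. In a select-all list these cases look alike: an unticked WORSE box does not separate no worsening from too early to tell.

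This matters because the trial is an acceptability pilot, perceived impact is one of its primary outcomes, and the feedback is meant to guide revision of the tool. A report that a given share of parents found the tool made surgery better, or that none found it made surgery worse, would describe something the respondents had not been through.

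**Working it through.** The plan gives no figure on this point, so the check sets the schedule, the items and the stated construct side by side.

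**1. What the family has experienced at the time of the survey.** The survey is completed in holding (D(3), D(5), Table 1). By then the family has had the education and the preoperative wait. Induction, surgery and emergence are still to come.

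**2. Which items can be answered at that time (Appendix B).**

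| Item | Answerable in holding? |
|---|---|
| Q1: link received, watched, with or without child | Yes |
| Q1: difficulty using or understanding the tool | Yes |
| Q1: child seemed more or less stressed; parent less stressed | Yes, these concern feelings ahead of surgery |
| Q1: understanding, questions answered, talking with the child | Yes |
| Q1: surgery experience BETTER / WORSE | No, not as worded |
| Q2: time spent | Yes |
| Q3: recommendation | Yes, but not from experience of induction or emergence |
| Q4-Q5: gaps and improvements (free text) | Yes, with the same limit as Q3 |

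So 2 of the 16 Q1 statements do not fit their timing. Q3 to Q5 fit, but their evidence base stops at the preoperative phase.

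**3. Item against construct.** D(4), which defines the outcome, speaks of the preoperative experience. The two items speak of the surgery experience. On the narrow D(4) construct the item wording is too wide; on the wider Background aim the timing is too early. The present text satisfies neither.

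**4. Whether a count can be attached.** D(4) gives an emergence delirium incidence of 30-50% in most studies and 10-80% overall, and says "ED can be extremely distressing for parents". Section I plans for 30 children per group. Then 30 × 0.30 = 9 and 30 × 0.50 = 15, with outer limits 30 × 0.10 = 3 and 30 × 0.80 = 24. If the cited incidence applied here, 9 to 15 (3 to 24) PIRA families would meet emergence delirium after giving their only rating. This counts families who meet the event. It does not count answers that are wrong or would change, because nothing in the documents links emergence delirium to a parent's rating of the tool.

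**The case against.** The best defense is that holding is a sensible time to rate preoperative education. Aim 2 concerns satisfaction and problems with the PIRA, not with surgery. D(4) names the preoperative experience, the survey part is headed as preoperative education, and the Background sentence lists what the tool might achieve and is not an endpoint. A rating taken after surgery would also mix opinion of the tool with how the operation went. This stands, and it supports keeping the survey where it is. It does not rescue the two items, whose wording goes beyond the construct it relies on.

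A reader might infer more than the documents support:

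- *That harm is under-counted and acceptability over-stated.* Ratings after surgery could fall, or rise if the tool prepared the family well. A difficult emergence is not in itself a harm caused by the tool.
- *That the gap list must omit the intraoperative and postoperative phases.* A parent who has viewed the tool can say in holding that induction or waking was unclear or not covered. Hindsight might add entries, but its absence does not exclude those topics.
- *That the main measure of harm is lost.* The protocol designates no such item. Statements on the child seeming more stressed and on difficulty with the tool are answerable in holding, and Q5 invites difficulties.
- *That 9 to 15 of 30 answers are affected.* As shown above, that figure counts expected delirium cases, not answers.
- *That emergence goes unmeasured.* The PAED covers it through a blinded nurse. Only the parent's view is missing.

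**Conclusion.** The point holds in a limited form. Two of 16 Q1 statements, both feeding a primary outcome, cannot be answered as worded when they are asked, and they disagree with the protocol's own description of that outcome. Recommendation and content-gap answers are valid for the preoperative phase but carry no experience of induction or emergence. The direction and size of any resulting bias are unknown. Utilization, the anxiety measures, the PAED and the sample size are untouched.

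This rests on two readings: that the survey is given once, since no second administration is described, and that the BETTER and WORSE items belong to the perceived-impact outcome. The second follows from D(5), which draws that outcome from Appendix B; Table 1 has no separate row for them.

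**What to change.** **Recommended.** Reword the two statements so that they refer to *my experience before surgery so far*, in line with D(4). State in the analysis plan that conclusions on perceived impact, recommendation and content gaps apply to the preoperative phase. The cost is a minor amendment and an edit to two REDCap fields. If any families have already answered the present wording, tabulate their answers to these two items separately. The rewording removes the not-yet-known reading of an empty box; a box left empty because the parent chose to skip it will still look like a no.

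**Optional, if the sponsor wants parent-perceived impact over the whole perioperative experience.** Add a short REDCap page before discharge that asks BETTER/WORSE about the surgery experience and repeats Q3 to Q5. Give it only after the PAED has been charted, so that it cannot unblind the PACU nurse. Report it alongside the holding-area answers, not in place of them, and update the timing in Table 1. The costs are some missing responses from parents occupied with a waking child, research-team time in recovery (none is described there now) or an emailed link, and ratings that partly reflect how surgery went. The last is the reason to keep both sets of answers.
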